# 11.4.3.3 Photopic Monocular UIVA

Photopic monocular uncorrected intermediate visual acuity (UIVA) at 66 cm in first implanted eyes will be summarized and analyzed using the methods described for UNVA.

#### 11.4.4 Secondary Performance Analyses

### 11.4.4.1 IOL Rotational Stability

For the first secondary performance endpoint, success for IOL rotational stability of the enVista MX60EFH trifocal IOL will be measured using the criteria for toric IOLs as stated in ISO 11979-7:2018 Section 6.2.2. Assessment of the secondary performance standard for the MX60EFH trifocal IOL will only be evaluated if all primary performance endpoints have demonstrated statistical success. If both of the following conditions are met, then IOL rotational stability of the enVista trifocal IOL will have been confirmed:

- At least 90% of the enVista trifocal IOLs will have rotated 10° or less at Visit 4(Day 120 to Day 180 after second eye IOL implantation)
- At least 95% of the enVista trifocal IOLs will have rotated 20° or less at Visit 4(Day 120 to Day 180 after second eye IOL implantation)

### 11.4.4.2 Change from Baseline in Photopic Monocular UNVA

Photopic monocular uncorrected near visual acuity (UNVA) at 40 cm at Baseline, at Post-Operative Visit 4 (Day 120 to 180 after second eye IOL implantation), and the Change from Baseline to Visit 4 will be summarized using continuous summary statistics in logMAR units

by treatment assignment for the first implanted eyes of ITT Set Subjects. A paired t-test will be used to test the statistical hypothesis for the Test lens group.

# 11.4.4.3 Change from Baseline in Photopic Monocular UIVA

Photopic monocular uncorrected intermediate visual acuity (UIVA) at 66 cm in first implanted eyes will be summarized and analyzed using the methods described for UNVA.

# 11.4.5 Subject Disposition

Enrollment status will be summarized in a table by investigator and overall. The number of randomized subjects will be summarized as well as the number and percentage of subjects that completed the entire trial, discontinued before implant, discontinued after the first implant but before the second surgery, and discontinued after the second surgery. In addition, for those subjects that did not complete the entire trial, the reason(s) for discontinuation will be summarized.

Accountability at each visit will be summarized. The accountability data will also be stratified by investigator and by treatment assignment.

Subjects and eyes in the Safety, ITT, PP, and PRO analysis sets will be summarized categorically by treatment and overall.

# 11.4.6 Demographics and Baseline Characteristics

Race, sex, ethnicity, and age will be presented by treatment group and overall in a Table.

#### 11.4.7 Protocol Deviations

The number of subjects within each type of protocol deviation will be presented using discrete summary statistics.

Major protocol deviations leading to exclusion from the PP Set will include the following:

- Ineligible subjects
- Subjects who received an incorrect IOL (for example, including but not limited to incorrect treatment group or incorrect lens model)
- Subjects who have had the first implanted eye IOL explanted prior to Visit 4
- Subjects without measured values for all of the primary performance endpoints at Visit 4, assessed within the Visit 4 window
- Subjects who have received an excluded prior or concomitant treatment that is likely to interfere with visual performance at Visit 4

Prior to unmasking, other criteria for major protocol deviations may be added.

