### **5.1.2** Performance Variables

The primary performance variables will be:

- Photopic uncorrected distance visual acuity (UDVA) for first implanted eyes at 4 m at Post-Operative Visit 4 (Day 120 to Day 180 after second eye IOL implantation)
- Photopic uncorrected near visual acuity (UNVA) for first implanted eyes at 40 cm at Post-Operative Visit 4 (Day 120 to Day 180 after second eye IOL implantation)
- Photopic uncorrected intermediate visual acuity (UIVA) for first implanted eyes at 66 cm at Post-Operative Visit 4 (Day 120 to Day 180 after second eye IOL implantation)

The secondary performance variables will be:

- IOL rotation for all trifocal eyes at Post-Operative Visit 4 (Day 120 to Day 180 after second eye IOL implantation)
- Change from baseline (preoperative) in uncorrected photopic near visual acuity (UNVA) at 40 cm for first implanted eyes to Post-Operative Visit 4 (Day 120 to Day 180 after second eye IOL implantation)
- Change from baseline (preoperative) in uncorrected photopic intermediate visual acuity (UIVA) at 66 cm for first implanted eyes to Post-Operative Visit 4 (Day 120 to Day 180 after second eye IOL implantation)

The supportive performance variables will be:(Data for these performance variables will be summarized by treatment group with descriptive statistics lacking hypotheses)

- Photopic corrected visual acuity (CDVA, DCNVA, and DCIVA) for first implanted eyes at Post-Operative Visit 4 (Day 120 to Day 180 after second eye IOL implantation)
- Photopic and mesopic binocular uncorrected near and intermediate visual acuity (UNVA and UIVA) at 40 cm and 66 cm, respectively, at Post-Operative Visit 4 (Day 120 to Day 180 after second eye IOL implantation
- Binocular CDVA defocus curves from +1.50 D to -3.50 D

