#### 9.1.5 Unscheduled Visit(s)

Additional visits may be scheduled, as necessary, to ensure the safety and well-being of subjects. All additional examinations should be fully documented in the source documents and on Unscheduled Visit CRFs, as appropriate. Visits intended to fulfill scheduled visit requirements that fall outside the designated scheduled visit window are not Unscheduled Visits. In these cases, the visit data will be collected and transcribed to the appropriate scheduled visit CRF.

If a subject is seen for multiple visits during a given visit timeframe, the data from the visit that is intended to meet the protocol requirements for the scheduled visit will be captured on the visit CRF. Where such a determination cannot be made, the first visit within the scheduled visit interval will be used for completion of the protocol required scheduled visit CRF. Data from any additional visits within a scheduled visit interval will be captured on an Unscheduled Visit CRF.

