#### 11.3.3 Per Protocol Set

The Per Protocol (PP) Set will include all bilaterally implanted subjects without major protocol deviations. Major protocol deviations are described in Section 11.5.7.

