### 11.4.3 Primary Performance Analyses

#### 11.4.3.1 Photopic Monocular UDVA

Photopic monocular uncorrected distance visual acuity (UDVA) at 4 m in first implanted eyes at Post-Operative Visit 4 will be summarized in logMAR units using continuous summary statistics by treatment group for the PP Set. Imputation of missing data is not conservative in non-inferiority testing. Therefore, missing data will not be imputed for the UDVA non-inferiority test. The treatment effect (mean Test [enVista trifocal] group IOL VA minus mean Control [enVista monofocal] group IOL VA) in logMAR units will be estimated in addition to a two-sided 90% confidence interval, using a statistical model with treatment and site as fixed factors. If the upper confidence limit (equivalent to a one-sided upper 95% confidence limit for the treatment effect) is less than 0.2 logMAR, then the Test enVista trifocal lens will be statistically non-inferior to the control enVista monofocal lens.

The previous continuous summary statistics will also be provided for the ITT Set. However, statistical success will not depend upon the results of the ITT analysis.

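### A valid in-window first-eye UDVA is dropped from the only set that decides UDVA non-inferiority when the Visit 4 UNVA or UIVA is missing.

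*Combined protocol and SAP*

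**What the plan says.** - **Endpoints.** Section 5.1.2 names three primary performance variables, all on the first implanted eye: "Photopic uncorrected distance visual acuity (UDVA) for first implanted eyes at 4 m at Post-Operative Visit 4"; "Photopic uncorrected near visual acuity (UNVA) for first implanted eyes at 40 cm at Post-Operative Visit 4"; and "Photopic uncorrected intermediate visual acuity (UIVA) for first implanted eyes at 66 cm at Post-Operative Visit 4".
- **PP Set.** Section 11.3.3: "The Per Protocol (PP) Set will include all bilaterally implanted subjects without major protocol deviations". It points to a Section 11.5.7 for the list of major deviations; the list is in Section 11.4.7.
- **Exclusion rule.** Section 11.4.7: "Major protocol deviations leading to exclusion from the PP Set will include the following", and one item is "Subjects without measured values for all of the primary performance endpoints at Visit 4, assessed within the Visit 4 window". The rule acts on the subject, not on the endpoint.
- **UDVA.** Section 11.4.3.1 tests non-inferiority on the PP Set with no imputation. It uses a model with treatment and site and compares the upper limit of a two-sided 90% interval with 0.2 logMAR. The ITT Set receives the continuous summary statistics, and then: "However, statistical success will not depend upon the results of the ITT analysis".
- **UNVA and UIVA.** Sections 11.4.3.2 and 11.4.3.3 decide these on the ITT Set, with MCMC multiple imputation of missing Visit 4 values.
- **Late visits.** Section 9.1.5, on scheduled visits held outside their window: "In these cases, the visit data will be collected and transcribed to the appropriate scheduled visit CRF".

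**The concern.** A missing 40 cm or 66 cm reading says nothing about whether the 4 m reading is sound. Yet it removes the 4 m reading from the one analysis that decides UDVA. For the two endpoints whose values are actually missing, the subject stays in the deciding analysis through imputation. The cost of a missing near or intermediate value thus falls on the distance endpoint.

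The exclusion also depends on something that happens after randomisation and may be related to the eye or the lens. A PP comparison that discards observed outcomes on that basis is no longer fully protected by randomisation. UDVA matters for the whole trial: all primary endpoints with success criteria must succeed (Sections 11.4 and 11.5.4), and rotational stability is evaluated only if they do (Section 11.4.4.1).

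A second, smaller gap follows. The ITT Set could show whether the exclusions matter, because it keeps these subjects and can include late Visit 4 values. For UDVA, however, Section 11.4.3.1 clearly promises only summary statistics on that set, not a confidence limit to set against 0.2.

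**Working it through.** **Inputs.** From Section 11.2.1.1: 100 Test and 50 Control evaluable subjects, SD 0.15 logMAR, margin 0.2, true difference 0, one-sided alpha 0.05. From Section 11.2.3: a 10% loss allowance, giving 112 + 56 = 168. The documents give no rate of missing UNVA or UIVA, so the rates below are assumptions.

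**1. The plan's own figure.** SE = 0.15 × √(1/100 + 1/50) = 0.0260. Noncentrality = 0.2/0.0260 = 7.7 on 148 df. Power from the noncentral t exceeds 99.99%, so the stated figure of more than 99% reproduces.

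**2. Does the rule cost power?** Assume a share of evaluable subjects in both arms is lost only because UNVA or UIVA is missing:

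| Share lost | n (Test/Control) | Power, true difference 0 | Power, true difference 0.10 (assumed) |
|---|---|---|---|
| 0% | 100/50 | >99.9% | 98.6% |
| 10% | 90/45 | >99.9% | 97.7% |
| 20% | 80/40 | >99.9% | 96.2% |

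Under the plan's assumptions, power is not the issue.

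**3. How far could selection move the estimate?** If a share q of one arm is dropped, and those subjects' mean UDVA differs by d from the subjects kept, then

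full-arm mean − retained mean = q × d.

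| q | d = 0.1 | d = 0.2 | d = 0.3 |
|---|---|---|---|
| 2% | 0.002 | 0.004 | 0.006 |
| 5% | 0.005 | 0.010 | 0.015 |
| 10% | 0.010 | 0.020 | 0.030 |

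To give q a scale: if UNVA and UIVA were each missing in 1% of subjects independently, 1 − 0.99² = 2.0% would lack at least one. At 5% each, 1 − 0.95² = 9.75%.

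**4. Direction.** The effect is Test minus Control, and a higher logMAR is worse. Dropping poor Test eyes lowers the estimate and favours non-inferiority. Dropping poor Control eyes raises it and works against non-inferiority. Dropping better-than-average eyes reverses each.

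**5. Could the conclusion change?** The one-sided 95% limit lies 1.655 × 0.0260 = 0.043 above the estimate (site terms ignored), so success needs an estimate below 0.2 − 0.043 = 0.157. Take the largest shift, 0.030, in the favourable direction and hold the half-width at 0.043. The PP result then succeeds where the full set would fail only if the full-set difference lies between 0.157 and 0.157 + 0.030 = 0.187. The lower end is 0.157/0.026 ≈ 6 standard errors from the planned difference of 0.

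**The case against.** **The effect is small.** This stands. The largest shift in the table assumes that 10% of an arm attends, gives a valid UDVA and still lacks another reading. The protocol's whole loss allowance is 10%.

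**One complete-case PP Set is a coherent choice.** It is fixed in advance, all primary endpoints must succeed together, and the same set supplies the supportive UNVA and UIVA summaries. That makes the rule defensible, but it does not give a reason to discard an observed 4 m value. The protocol's reason for not imputing UDVA, that imputation is not conservative for non-inferiority, argues against creating values, not against using observed ones.

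**The item could be read as covering only subjects who lack all three values.** On that reading the problem disappears. Nothing else in the protocol supports it, and doubt about who enters a deciding analysis is itself a reason to reword.

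Three stronger readings are tempting, and the documents do not support them:

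- *That the rule pushes the result towards success.* The direction depends on which arm loses eyes. Section 10.3 expects Control subjects to need correction for near and intermediate vision, so any difficulty with those tests could fall more on Control. Nothing shown says that a poor near result becomes a missing one, and the testing methods in Appendix B are not shown in the text available.
- *That out-of-window near or intermediate readings are a second common route.* Appendix A schedules all three acuities at the same Visit 4. A wholly late visit puts UDVA out of window too, and a window is an ordinary PP criterion. A valid UDVA with a late UNVA or UIVA needs Visit 4 to be split across days.
- *That excluded and late values appear nowhere.* Section 11.4.3.1 provides ITT summary statistics, and nothing in Section 11.3.1 removes such values. With n, mean and SD by arm, a reader could form an approximate unadjusted limit. What is missing is a clearly stated ITT confidence limit against the margin.

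**Conclusion.** The point holds, with low severity. On the natural reading of Section 11.4.7, a subject with a valid in-window first-eye UDVA leaves the only set that decides UDVA non-inferiority because UNVA or UIVA is missing at Visit 4. The documents contain no exemption, and Section 11.4.7 provides only for adding criteria before unmasking.

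The consequence is possible selection bias of unknown sign. Its size rests on assumed rates: 2% to 10% of one arm affected, differing by 0.1 to 0.3 logMAR, gives 0.002 to 0.030 logMAR. The top of that range is about 70% of the 0.043 half-width (0.030/0.043) but 15% of the 0.2 margin (0.030/0.2). The estimate could therefore be touched, but a reversed conclusion is unlikely unless the true difference is far from the planned value of 0. Separately, ITT UDVA has no clearly stated confidence limit to set against the margin.

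**What to change.** 1. In Section 11.4.7, make the availability criterion endpoint-specific. Suggested wording: for the UDVA analysis, exclude subjects without a measured first-eye UDVA within the Visit 4 window; a missing UNVA or UIVA does not by itself exclude a subject from that analysis.
2. In Section 11.4.3.1, pre-specify a supportive repeat of the same treatment-plus-site model on all observed ITT first-eye UDVA values, including out-of-window Visit 4 values. Report the two-sided 90% interval against 0.2. It need not decide success.
3. In the same edit, correct the cross-reference in Section 11.3.3 to Section 11.4.7.

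Cost: a line or two of wording and one rerun of an existing model. The PP Set used for UDVA may differ slightly from the one behind the supportive UNVA and UIVA summaries, so the tables should give n for each endpoint. Section 11.4 provides for a SAP to be approved before database lock and to note changes from the protocol, so the changes can be recorded there.

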### 11.5 Additional Statistical Considerations

# 11.5.1 Handling of Missing Data

Unless otherwise specified, missing data will not be imputed.

#### 11.5.2 Multicenter Issues

Randomization will be stratified by site.

#### 11.5.3 Interim Analyses

No interim analyses are planned. There are no plans to stop the study early on statistical grounds.

# 11.5.4 Multiplicity Issues

As all primary performance endpoints with success criteria described in Section 11.1 are required to demonstrate statistical success, adjustment for multiplicity is not necessary for these endpoints.

Statistical testing of the secondary endpoint with a success criterion (IOL rotational stability) will not be evaluated for success unless all primary endpoints with success criteria are met. Change from baseline in UNVA and UIVA are exploratory endpoints and will not be adjusted for multiplicity. Primary and secondary endpoints without success criteria will not affect the evaluation of secondary endpoints with success criteria. Therefore, adjustment for multiplicity is also not necessary for these endpoints.

Any statistical tests of endpoints that are not primary or secondary endpoints will be considered exploratory and will not be adjusted for multiplicity.

# 12 QUALITY CONTROL AND QUALITY ASSURANCE

# 12.1 Study Monitoring

The Sponsor and its representatives must be allowed to visit all study site locations to assess the data, quality, and study integrity in a manner consistent with applicable HC and local authority regulations and the procedures adopted by the Sponsor or its representative.

Prior to the start of the study, member(s) of the Sponsor (or designees) will review the protocol, CRF, regulatory obligations, and other material or equipment relevant to the conduct of the study with the Investigator/Sub-Investigator and relevant study site personnel.

Monitoring visits and telephone consultations will occur as necessary, as per the monitoring plan, during the course of the investigation to verify the following:

- The rights and well-being of subjects are protected
- The conduct of the investigation is in compliance with:
  - > The content of this protocol,

➤ ISO 14155:2020 (E) Clinical Investigation of Medical Devices for Human Subjects – Good Clinical Practice,

and in accordance with:

- ➤ ISO 11979-7:2018 Ophthalmic implants Intraocular lenses Part 7: Clinical investigations of intraocular lenses for the correction of aphakia,
- ➤ ISO/TR 22979 (2017) Ophthalmic implants Intraocular lenses Guidance on assessment of the need for clinical investigation of intraocular lens design modifications,
- > ANSI Z80.12-2007 (R2017), and
- Applicable national and local medical device regulations and standards.
- The integrity of the data, including adequate study documentation
- The facilities remain acceptable
- The Investigator and site personnel remain qualified and able to conduct the study
- Test article accountability

During the study, if the Sponsor (or designee) determines that an Investigator is non-compliant with the study plan and/or applicable regulatory requirements, the Sponsor (or designee) will take remediation action to secure compliance. In addition, the Sponsor may terminate the Investigator's participation in the study, if appropriate, if the Investigator remains non-compliant despite the remediation actions.

#### 12.2 Source Documentation

All medical information obtained at each study visit must be recorded in the subject's record (source documentation) in real-time as it is collected. Source documentation consists of original subject documents, as well as data and records with information relevant to the subject and his/her participation in the study.

Source documentation worksheets may be provided by the Sponsor or its designee to record pertinent information. The completed worksheets can then be incorporated into the subject's medical chart. If it is preferred not to use the worksheets in the subject's permanent record, then the worksheets should be used as a reference to determine the type of study data to record in the subject's permanent record.

# 12.3 Case Reports Forms and Data Verification

As used in this protocol, the term Case Report Form (CRF) refers to an element of an EDC system and should be understood to refer to an electronic data record developed as part of the electronic data capture method utilized in this study.

Subject data required by this protocol are to be recorded on CRFs. The Investigator and his/her study site personnel will be responsible for completing the CRFs in a timely manner. The Investigator is required to verify that all of the requested information is accurately recorded on the CRFs. All information requested on the CRFs needs to be supplied, including subject identification and initials, date(s), assessment values, etc., and any omission or discrepancy will require explanation. All information on CRFs must be traceable to source documents.

The study monitor will be responsible for reviewing and verifying the data recorded on the CRFs utilizing the original and all source documentation and querying discrepant findings. The Investigator and study site personnel will be responsible for answering all queries in a timely manner.

# 12.4 Recording of Data and Retention of Documents

Subject data recorded on CRFs during the study will be documented in a coded fashion. The subject will only be identified by the unique subject number. Confidentiality of subject records must be maintained to ensure adherence to applicable clinical practice standards and local privacy regulations.

The Investigator must retain essential documents indefinitely after the completion of the study, unless otherwise notified by the Sponsor. The Investigator agrees to adhere to the document retention procedures when signing the protocol Investigator Statement of Approval.

Essential documents include, but are not limited to, the following:

- IRB/IEC approvals for the study protocol, all amendments, ICF(s), and advertisements
- IRB/IEC annual study review
- IRB/IEC correspondence and reports (e.g., SAE reports, protocol deviations, and safety updates)
- Regulatory documents (e.g., financial disclosure and delegation of authority forms)
- All source documents
- CRFs
- Subject's signed ICF
- Device Investigator Agreement
- Accountability records for the test article(s)
- Correspondence from and to the Sponsor and CRO
- Any other documents relevant to the conduct of the study

In the event the Investigator withdraws from the study (e.g., retirement or relocation), study records will be transferred to a mutually agreed upon designee (e.g., another Investigator or the site IRB/IEC). The Investigator will provide notice of such transfer in writing to the Sponsor and/or its representative.

# 12.5 Audits and Inspections

Audits of clinical research activities in accordance with the Sponsor's internal Standard Operating Procedures (SOPs) to evaluate compliance with ISO 14155:2020 and the principles of GCP may take place. A regulatory authority also may wish to conduct an inspection during the study or after its completion. If an inspection is requested by a regulatory authority and/or IRB/IEC, the Investigator must inform the Sponsor and its representative immediately that this request has been made.

